### 10.4 Handling of Dropouts or Missing Data

In general, missing data will not be imputed. Summary data for observed cases only will be presented.

For weekly assessments derived from daily eCOA data, the weekly values will be considered missing if there are less than 4 days with data assessed within a week.

For the primary endpoint, overall response, subjects must have at least 4 evaluable weeks of data. An evaluable week is one in which there are at least four 24-hour daily records of abdominal pain score, number of CSBMs, and Bristol stool chart. If number of CSBMs for a date is 0, then Bristol stool chart data is expected to be missing. The day will still count towards the 4-day minimum. Subjects with less than 4 evaluable weeks of data will be considered non-responders.

Mixed model repeated measures (MMRM), which provide valid parameter estimates even with some values missing, will be used to analyze continuous assessments taken over time.

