5.3 Treatment assignment procedures

5.3.1 Randomisation

This is a double-blind study and subjects will randomly receive either Blautix[™] or placebo in a 1:1 ratio respectively. At Baseline (Visit 1), subjects will be classified into either the IBS- C (Cohort C) or the IBS-D (Cohort D) cohort of subjects and 250 subjects will be enrolled into each cohort. Within each cohort, 125 subjects will randomly receive Blautix[™] and 125 subjects will randomly receive matching placebo. Allocation of randomisation numbers will be performed centrally using an interactive voice/web response allocation system (IV/WRS).

Subjects, 4D pharma Plc, designated CRO and clinical site staff will be blinded to the investigational product allocation for each subject. Randomisation data will be kept strictly confidential, filed securely by the Sponsor (or designee) and accessible only to authorised persons of the Sponsor (or designee), and accessible only to authorised per Sponsor (or designee)'s standard operating procedures (SOPs) until the time of unbinding.

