10.2 Sample Size Calculation

Within each Cohort, 125 subjects per treatment group provide at least 80% power to demonstrate a statistically significant difference between the treatment groups at a one-sided alpha of 10% using Pearson's test with Yates's correction when the true response rate in Placebo group is 40% and the true response rate in the BlautixTM group is 55%.

The total planned study size is therefore 500 subjects.

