10.7 Handling of Missing Data

Subjects who do not provide enough data to enable assessment of whether that subject is a responder will be deemed a non-responder.

An 'evaluable week' is one in which there are at least four twenty-four hour (4 day) records of abdominal pain score and at least four daily records of the number of complete spontaneous bowel movements and Bristol stool chart.

If a subject has not provided four evaluable weeks of data, then they are deemed to be a non-responder.

If a subject has provided at least four evaluable weeks of data then they are deemed to be a responder if they have reported an improvement in their weekly symptoms for $\ge 60\%$ of the

evaluable weeks (if the total number of evaluable weeks is four, five or six) or for \geq 50% of the evaluable weeks (if the total number of evaluable weeks is seven or eight).

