#### 10.1.1 Primary Efficacy Endpoint

The primary efficacy endpoint is whether the subject is an overall responder. The definition of an overall responder is IBS subtype specific and consists of two components.

For both IBS subtypes, the first component of overall response is the weekly average of Abdominal Pain Intensity (0-10, 0=none, 10=worst possible pain) over the past 24 hours. Improvement for the week is defined as a decrease of at least 30% compared with baseline.

For the IBS-C subtype, the second component of overall response is the stool frequency per week. Improvement is defined as an increase of 1 or more complete spontaneous bowel movements (CSBMs) per week compared with baseline. The number of bowel movements is recorded once per day in the eCOA device, including zeroes.

For the IBS-D subtype, the second component of overall response is the proportion of days per week with at least one stool with a consistency of Type 6 or 7 on the Bristol Stool Chart. Improvement is defined as a decrease in the proportion of at least 50% compared with the proportion during the 7-day period before baseline used to determine eligibility. Stool consistency is recorded for each bowel movement in the eCOA device, so more than one entry per day may exist. The daily result should be reduced to whether a Type 6 or Type 7 was included on that date.

A subject will be considered a responder only during weeks for which both components indicate improvement. Subjects must have at least 4 evaluable weeks of data as defined in [Section 10.4](#) for each of the instruments used to determine response. Subjects with less than 4 evaluable weeks of assessments available during the treatment period will be considered as non-responders for overall response.

Subjects who have at least 7 evaluable weeks of data and have reported an improvement in their weekly symptoms for  $\geq 50\%$  of the treatment period will be considered overall responders. Subjects who have 4, 5, or 6 evaluable weeks of data must show improvement for  $\geq 60\%$  of the treatment period to be deemed overall responders.

The days for each week will be taken as calendar days from the Day 1 date (randomisation date).

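### The evaluable-week rule demands a diary item that each cohort's endpoint does not use, so weeks with a fully observed endpoint can be discarded; the size is unknown and probably small

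*SAP*

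**What the plan says.** SAP 10.1.1 builds weekly response from two components. Pain is common to both cohorts. The second is the weekly CSBM count in IBS-C, and the proportion of days with a Type 6 or 7 stool in IBS-D.

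SAP 10.4 then decides which weeks count, without separating the cohorts: "An evaluable week is one in which there are at least four 24-hour daily records of abdominal pain score, number of CSBMs, and Bristol stool". It adds a waiver: "If number of CSBMs for a date is 0, then Bristol stool chart data is expected to be missing", and such a day still counts toward the four.

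Protocol 10.7 asks for four pain records and "at least four daily records of the number of complete spontaneous bowel movements and Bristol stool chart". It has no waiver.

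SAP 10.1.1 asks for four evaluable weeks, as Section 10.4 defines them, "for each of the instruments used to determine response".

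Under protocol 10.7, fewer than four evaluable weeks means non-response. Four to six require improvement in at least 60% of them, and seven or eight require at least 50%.

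**The concern.** The rule tests for more than the endpoint needs. In Cohort C, a day with a pain score and a CSBM count holds everything the endpoint uses, yet it can fail for want of a Bristol rating. In Cohort D, a day with pain and Bristol ratings can fail for want of a CSBM count.

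The SAP waiver raises a second issue. Taken literally, a Cohort C day with pain and count recorded can fail the Bristol requirement only if it has at least one CSBM. More CSBMs is what Cohort C counts as improvement, so good weeks (those meeting both improvement criteria) would be more exposed than bad ones.

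At stake is the classification of borderline subjects on the primary endpoint. The protocol and SAP could also classify the same diary differently.

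**Working it through.** **1. The plan's own power figure.** Inputs from protocol 10.2: 125 per arm, 40% against 55%, one-sided alpha 10%, Yates-corrected Pearson test. Allocation is 1:1 (protocol 5.3.1).

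- Uncorrected n per arm = [1.2816·√(2·0.475·0.525) + 0.8416·√(0.40·0.60 + 0.55·0.45)]² / 0.15² = (0.905 + 0.588)² / 0.0225 ≈ 99.0, so 100.
- With continuity correction: (99.0/4)·[1 + √(1 + 4/(99.0·0.15))]² ≈ 112.
- Exact power at 125 per arm: 82.5% with Yates, 85.6% without.

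The protocol's claim of at least 80% reproduces.

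**2. Required against used.**

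| | Endpoint uses | SAP 10.4 requires | Protocol 10.7 requires |
|---|---|---|---|
| Cohort C | pain, CSBM count | pain, count, Bristol (waived if count is 0) | pain, count, Bristol |
| Cohort D | pain, Type 6/7 days | same | same |

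**3. What one lost week does**, counting over evaluable weeks as protocol 10.7 does.

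- Good week lost: 4/8 becomes 3/7 = 43%, below 50%. 4/7 becomes 3/6 = 50%, below 60%. Both become non-responders.
- Bad week lost: 4/8 becomes 4/7 = 57%, above 50%. 4/7 becomes 4/6 = 67%, above 60%. Both stay responders.

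**4. Chance that a Cohort C week is lost only through missing ratings (literal SAP text).** Let k be CSBM days in the week and q the chance that the rating is missing on such a day. Both are assumptions, and days are taken as independent.

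- Full seven-day diary: P(lost) = P(Bin(k, q) ≥ 4). This is exactly 0 for k ≤ 3. For k = 5 it is 0.05% at q = 10% and 3.1% at q = 30%. For k = 7 it is 0.02%, 0.27% and 3.3% at q = 5%, 10% and 20%.
- Three diary days already missing: only four days remain, so one missing rating loses the week. P(lost) = 1 − E[(1 − q)^J], where J is the number of CSBM days among the four kept. At q = 5% it is 2.9% for k = 1 (4/7 × 0.05), 8.4% for k = 3 and 13.6% for k = 5.

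**5. Sparse diaries.** Assume each day's diary is completed with probability 65%, and the unneeded item is missing on 10% of exposed days.

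- Cohort D, count missing on any day: evaluable weeks fall from P(Bin(7, 0.65) ≥ 4) = 80.0% to P(Bin(7, 0.585) ≥ 4) = 68.1%. Subjects with fewer than 4 of 8 evaluable weeks rise from 1.0% to 7.4%. At 75% completion, evaluable weeks fall from 92.9% to 83.9%.
- Cohort C with the waiver and CSBMs on 3 of 7 days: three days at 0.585 and four at 0.65 give 75.2% evaluable weeks, and P(Bin(8, 0.752) ≤ 3) = 2.6% of subjects below four. At 90% completion, evaluable weeks fall from 99.7% to 99.1%.

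**6. Effect on rates and power in Cohort C.** The simulation used 125 per arm, tuned to about 40%/55% under a cohort-specific rule. It took q from 2% to 30%, 10% or 25% of diary days missing, and CSBM days in good against bad weeks of 3 v 1, 4 v 1.5 or 6 v 2: 30 scenarios on the literal SAP text.

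| q | Diary days missing | CSBM days, good v bad | Good weeks lost | Bad weeks lost |
|---|---|---|---|---|
| 5% | 10% | 3 v 1 | 0.25% | 0.07% |
| 5% | 25% | 4 v 1.5 | 2.3% | 0.9% |
| 20% | 25% | 6 v 2 | 19.2% | 5.0% |

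- Good weeks were lost about 3 to 9 times as often as bad ones.
- For q up to 5%, response rates fell by 0 to 1.3 points per arm.
- In 29 of the 30 scenarios power fell by no more than 1.6 points.
- In the remaining one (q = 30%, 25% missing, 6 v 2) the rates fell to 27.8%/40.0% and power from 81% to 74%.

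**The case against.** A reader might infer that the rule is an established outcome-dependent filter that discards good Cohort C weeks on a large scale. The documents do not support that, for these reasons.

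- **The waiver's wording.** A day with only incomplete or laxative-assisted stools has zero CSBMs but still has stools to rate. Expecting the Bristol record to be missing makes most sense if the SAP means zero bowel movements, which is what SAP 10.1.1 says the device records. Then any day with a stool can fail, and the asymmetry shrinks.
- **The protocol may point the other way.** Protocol 10.7 has no waiver. If stool-free days carry no Bristol record, constipated weeks would be the ones lost.
- **SAP 10.1.1 may already restrict the rule** to the instruments that determine response. This does not settle it, because the sentence refers back to Section 10.4, which names all three records.
- **Missing ratings may be rare.** Protocol 7.1 has subjects reminded to rate every stool before entering the count. Neither document says whether the device enforces this.
- **Alarming figures need unfavourable inputs.** With five diary days, a CSBM on each and 10% to 30% of ratings missing, the chance of an evaluable week is 92% to 53% (P(Bin(5, 0.9) ≥ 4) and P(Bin(5, 0.7) ≥ 4)). Scaled as in SAP 10.1.1, that is at least 7 CSBMs per week in subjects enrolled with fewer than 3. With a full diary the same five CSBM days give 99.95% to 96.9%.
- **The count is not useless in Cohort D.** It separates a day without stool from a day with unrated stools. A recorded zero is enough for that.

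These points limit direction and size. They do not remove the mismatch between what the rule demands and what each endpoint uses, or the disagreement between the documents.

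**Conclusion.** The concern holds in conditional form. Both documents require records beyond those that determine response, so weeks with a fully observed endpoint can be lost and a borderline responder reclassified. SAP 10.1.1, SAP 10.4 and protocol 10.7 do not agree on the rule.

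That good Cohort C weeks are lost more often follows only from the literal SAP text, with some ratings missing on CSBM days at a rate unrelated to outcome. The size is unknown because no missing-rating rate is given. It is probably small: 0 to 1.3 points per arm at up to 5% missing ratings, and usually 0 to about 1.5 points of power. These figures rest on assumed diary completion, CSBM days and within-subject correlation.

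The rule is the same in both arms, so it does not inflate type I error when the arms are equal. The expected harm is lower Cohort C response rates with a modest loss of power. For Cohort D only the sparse-diary illustration in step 5 was computed.

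**What to change.** Before any unblinding, including the interim analysis in protocol 10.3 and SAP 10.5, define the evaluable week by cohort in SAP 10.4 and protocol 10.7, and align SAP 10.1.1.

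- **Cohort C:** at least 4 days with a pain score and a CSBM count, zero included.
- **Cohort D:** at least 4 days with a pain score and either a Bristol rating or a recorded zero bowel movements.

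This keys the waiver to zero bowel movements. It also closes a gap in the literal SAP text, under which a Cohort D day with stools, no CSBM and no rating would count although the endpoint's own instrument is missing. The SAP should also state whether the device accepts a count without ratings.

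With this rule no week is lost for want of an unused record, so this source of loss disappears and the planned 40%/55% and 82.5% exact power are untouched by it. No new data are needed. The cost is wording, derivation code and a documented change to the primary-endpoint derivation in both documents, which is why it must be dated before unblinding.

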### 10.5 Interim Analysis and Data Monitoring

After approximately 250 subjects have completed 8 weeks of treatment, an interim analysis will be conducted. This unblinded interim analysis will be provided to the Chief Scientific Officer (CSO) at 4D pharma. These analyses will be conducted by an unblinded study team, independent of the study team, as documented in the Unblinding Plan.

Summary tables for disposition, demographics and baseline characteristics, safety data, and other pertinent study data (e.g., concomitant medications and study drug exposure/compliance) will be constructed with treatment groups masked, yet unblinded.

The efficacy tables will consist of the table for the primary efficacy analysis and the tables covering additional analysis of the primary efficacy endpoint. The secondary analysis tables for stool consistency and frequency will also be included.

The assignment to masked treatment group will be done at random by an unblinded statistician and labeled in a way that masks treatment (e.g., Treatment A, Treatment B.).

The protocol describes an interim analysis of the unblinded efficacy data with early stopping for futility. It has been decided that the trial will not be stopped for futility.

The DSMB will not review the interim analysis. The DSMB will be presented the final study results after unblinding and database lock.

## 10.6 Examination of Subgroups

The summary and analysis of the primary efficacy endpoint (overall response) will be repeated for subgroups of sex and region (US, UK and Ireland).

The CMH analysis of overall response stratified by subtype will also be presented by sex and by region.

## 10.7 Multiple Comparison/Multiplicity

No adjustments for multiplicity will be made in this study.

## 10.8 Multicenter Studies

This is a multicenter study, having about 30 centers participating in the study. Only about 8 of these centers have high enrollment, with relatively low enrollment at the other centers. The low number of subjects at many centers does not allow the center to be included as a factor in statistical models. Region (US, UK and Ireland), will be used in supplemental analysis of the primary efficacy endpoint and in secondary efficacy analyses as specified.

# 11. METHODS OF EFFICACY ANALYSIS

## 11.1 Primary Efficacy Analyses

For the primary analysis of the overall response rate, as defined in [Section 10.1.1](#), the following one-sided hypotheses will be tested with a significance level  $\alpha=0.10$ :

$$H_0: \pi_T - \pi_P \leq 0 \leftrightarrow H_1: \pi_T - \pi_P > 0$$

where  $\pi_T$  and  $\pi_P$  are the proportions of overall responders under active treatment and placebo after 8 weeks of treatment, respectively. The hypotheses will be tested using the FAS using Pearson's chi-square test with Yates' continuity correction. As this is a one-sided chi-square test, the p-value from

the test will be divided by two if the difference is in favor of the Blautix arm ( $\pi_T > \pi_P$ ) and divided by two then subtracted from 1 if the difference is in favor of the placebo arm ( $\pi_T \leq \pi_P$ ).

The test will be applied separately to each IBS subtype.

Summary statistics will show the frequency of overall responders in each subtype and treatment group, the percentage of responders in each treatment group within subtype, the treatment difference in percentages within each subtype (active – placebo), and 80% Wald (asymptotic) confidence intervals, with continuity correction, for the differences in percentages.

## 11.2 Additional Analyses of the Primary Efficacy Endpoint

As a sensitivity analysis, the primary efficacy analysis of the overall response rate will be repeated for the Efficacy Evaluable Set.

The remaining additional summaries and analyses will be done using the FAS.

The overall response rate will be analyzed with the IBS subtypes combined. A CMH test stratified by subtype will be used to test for an overall difference between the treatment groups across the subtype strata. To correspond with the primary analysis, the significance level will be two-sided 0.20 and an 80% CI for the treatment difference will be provided.

The primary efficacy endpoint (overall response) will be summarized and analyzed using the same method as the primary analysis by subgroups formed by sex and by region (US, UK and Ireland). The CMH analysis of overall response stratified by subtype will also be presented by sex and by region.

The frequencies and percentages of responders and non-responders by week during the treatment period will be summarized by IBS subtype and treatment group. A summary for the subtypes combined will be included. No CIs or inferences will be given.

The overall response rate will be further analyzed using a logistic regression model for each subtype. The models will include treatment and region (US, UK and Ireland) as factors and the baseline week average of Abdominal Pain Intensity and the subtype-specific baseline value as covariates. For the IBS-D model, the baseline covariate will be the proportion (as %) of days during the consecutive week prior to baseline, used for assessment of eligibility assessment, with at least one bowel movement Type 6 or 7. For the IBS-C model, the baseline covariate will be the average stool frequency in the week prior to baseline as noted for IBS-D. Model based odds ratios will be reported with 95% CIs.

The weekly average Abdominal Pain Intensities, the Abdominal Pain Intensity differences (baseline – weekly average, such that positive differences indicate improvement), and the percent differences [ $100 * (\text{baseline} - \text{weekly average}) / \text{baseline}$ ] will be summarized by IBS subtype (including combined), treatment group, and week across the treatment period and follow-up.

The weekly average Abdominal Pain Intensity differences during the treatment period (not including follow-up) will be further analyzed using linear models for repeated measures. The models will include treatment, region, and week as main effects, treatment-by-week as an interaction term, and the baseline week Abdominal Pain Intensity as a covariate. Separate models will be built for each IBS subtype and for the subtypes combined. The IBS subtype will be included in the model for combined subtypes as a fixed effect. The covariance matrix will be unstructured. If there are convergence issues, corrected AIC will be used to

choose between the following covariance structures: Toeplitz, heterogeneous autoregressive (1) [ARH(1)] and autoregressive(1) [AR(1)]. The method of Kenward and Roger will be used to estimate denominator degrees of freedom.

Least squares (LS) means and their standard errors (SE) from the MMRM models for the weekly average Abdominal Pain Intensity differences by IBS subtype, treatment group, and week with 95% CIs will be presented. The LSM and SE of the treatment differences from placebo will also be presented with 95% CIs and p-values from t-tests for a difference from 0.

Listings of daily assessments from the eCOA data will not be provided. However, the derived weekly endpoints and response rates will be listed by IBS subtype and treatment group.

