3.2 Endpoints

Primary Efficacy Endpoint

The primary efficacy endpoint is whether the subject is an overall responder.

A subject is an 'overall responder' if they have reported an improvement in their weekly (Cohort specific) symptoms for \geq 50% of the treatment period (4 out of 8 weeks).

	IBS-C	IBS-D	
Primary Endpoint Responder Symptom Definition	Abdominal Pain Intensity Decrease in weekly average of worst abdominal pain in the past 24 hours score of at least 30% compared with baseline	Abdominal Pain Intensity Decrease in weekly average of worst abdominal pain in past 24 hours score of at least 30% compared with baseline	
	And Stool Frequency	and Stool Consistency (BSS)	
	Increase of 1 or more Complete spontaneous bowel movements (CSBM) per week compared with baseline.	Decrease at least 50% in the proportion of days per week with at least one stool that has a consistency of Type 6 or 7 compared with baseline.	

Secondary Efficacy Endpoints

- Subject global assessment of relief
- Stool consistency/frequency
- IBS-QOL
- IBS-SSS
- HADS

Exploratory Endpoints

Safety Endpoints

- Incidence, nature, severity, relatedness, seriousness, expectedness and outcome of adverse events
- Haematology and blood chemistry assessments
- Vital signs

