10.5.2 Secondary Efficacy Analysis

Primary Endpoint:

[figure not shown]
Secondary Analyses of the Primary Endpoint will include the use of baseline characteristics as covariates and analyses using the Efficacy Evaluable Analysis Set.

Secondary Efficacy Endpoints:

Secondary efficacy endpoints will be compared between the two treatment groups within each Cohort using Pearson's test with Yates's correction, the Mann Whitney test or other standard statistical tests as appropriate.

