## 5. DETERMINATION OF SAMPLE SIZE

Within each cohort (IBS-C or IBS-D) 125 subjects per treatment group (Blautix™ or Placebo) will provide at least 80% power to demonstrate a statistically significant difference in response rate between treatment groups at a one-sided alpha of 10% using Pearson's test with Yates' correction when the true response rate in the Placebo group is 40% and the true response rate in the Blautix™ group is 55%.

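### No visible inferential analysis uses the number of improved weeks; one pre-specified supportive rank analysis would add useful information at little cost, with the primary test unchanged

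*SAP*

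**What the plan says.** Protocol 3.2 defines the endpoint as binary: "The primary efficacy endpoint is whether the subject is an overall responder", meaning improvement in both components in at least 4 of 8 weeks. Protocol 10.7 and SAP 10.1.1 modify the cut for incomplete diaries. Subjects with 4 to 6 evaluable weeks need at least 60%, those with 7 or 8 need at least 50%, and those with fewer than 4 are non-responders.

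SAP 11.1 tests π_T against π_P, which "are the proportions of overall responders under active treatment and placebo after 8 weeks of treatment, respectively", with a Yates-corrected chi-square test in each subtype at one-sided 0.10. SAP 11.2 then adds the Efficacy Evaluable repeat, a CMH test stratified by subtype, sex and region subgroups, and logistic models. All of these use the same binary status. For weekly responder frequencies it says: "A summary for the subtypes combined will be included. No CIs or inferences will be given".

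Other weekly data are tested. SAP 11.2 has an MMRM of weekly pain with 95% CIs and p-values, and SAP 11.3.2 has Mann-Whitney tests on CSBM changes. The content of the exploratory analyses (Protocol 10.5.3, SAP 10.1.3 and 11.4) is not visible.

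**The concern.** With complete data, the cut treats 4 improved weeks like 8, and 3 like 0. The discarded ordering is already in the database: SAP 10.1.1 derives weekly response and SAP 11.2 lists it. The pain and CSBM analyses do not replace it, because they look at one component at a time and response requires both in the same week.

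Protocol 10.3 says the results will guide planning of pivotal trials. For that purpose it matters whether Blautix gives more weeks of relief or only carries some subjects over the threshold. If a cohort's responder result falls near the 0.10 boundary, the visible plan offers no inference on joint response beyond the cut. SAP 6 labels anything added after the blind is broken as post hoc and exploratory, so such an analysis has to be specified beforehand to carry weight.

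**Working it through.** **Inputs.** Protocol 10.2: "125 subjects per treatment group provide at least 80% power", at one-sided 0.10. SAP 5: "when the true response rate in the Placebo group is 40% and the true response rate in the Blautix™ group is 55"%. Allocation is 1:1. The documents give neither a distribution of improved weeks nor a within-subject correlation, so both are assumed below and varied.

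**Step 1: the plan's own figure.** With p̄ = (0.40 + 0.55)/2 = 0.475 and n = 125 per arm:

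z = [(0.15 − c)·√125 − 1.2816·√(2·0.475·0.525)] / √(0.40·0.60 + 0.55·0.45)

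- No correction (c = 0): (1.677 − 0.905)/0.698 = 1.106, power 86.6%.
- Yates (c = 1/125 = 0.008): (1.588 − 0.905)/0.698 = 0.978, power 83.6%.
- Exact binomial enumeration: 85.6% uncorrected and **82.5% with Yates**.

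The stated power of at least 80% holds. Yates costs 85.6 − 82.5 = 3.1 points.

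**Step 2: rank test on 0-8 improved weeks.** The count is beta-binomial over 8 weeks, with all weeks evaluable. The placebo mean is set so that P(at least 4) = 0.40. Two forms of benefit both give 0.55 on Blautix:

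- *Common shift*: the weekly response probability rises for everyone.
- *Switch*: 15% of subjects move from the non-responder to the responder distribution, with no change within either group. Placebo probabilities for 0-3 weeks are multiplied by 0.45/0.60 and those for 4-8 weeks by 0.55/0.40.

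Power of the tie-corrected Mann-Whitney test, one-sided 0.10, 125 per arm, 200,000 simulated trials:

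| Correlation | Common shift | Gain over Yates (82.5%) | Gain over uncorrected (85.6%) | Switch |
|---|---|---|---|---|
| 0.2 | 94.5% | 12.0 | 8.9 | 78.7% |
| 0.5 | 94.2% | 11.7 | 8.6 | 79.0% |
| 0.7 | 92.8% | 10.3 | 7.2 | 80.5% |
| 0.8 | 91.4% | 8.9 | 5.8 | 81.8% |
| 0.9 | 89.4% | 6.9 | 3.8 | 83.6% |

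Type I error of the rank test is about 10%. An equal mix of the two forms gives 87-89%. At 40% v 50% under a common shift, Yates has 55.9% and the rank test 69-74% for correlations of 0.2-0.8. If 10-20% of each arm is forced to zero improved weeks while 40% and 55% are kept, the rank test has 89.5-93% under a shift.

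The switch case loses for a simple reason. The probability that a Blautix subject does better, ties counted half, is then 0.5 + 0.15/2 = 0.575, the same as for the binary outcome. The extra ordering adds only noise. Under a common shift it is about 0.59-0.60 for correlations of 0.2-0.8.

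**Step 3: does a 0-8 count match the endpoint?** Under Protocol 10.7:

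| Evaluable weeks | Fewest improved weeks for a responder | Most for a non-responder |
|---|---|---|
| 4 | 3 (75%) | 2 (50%) |
| 5 | 3 (60%) | 2 (40%) |
| 6 | 4 (67%) | 3 (50%) |
| 7 | 4 (57%) | 3 (43%) |
| 8 | 4 (50%) | 3 (38%) |

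A raw count ties a responder with 3 of 4 or 3 of 5 to a non-responder with 3 of 6, 7 or 8, because it counts missing weeks as failures. The proportion of evaluable weeks follows the protocol's denominator. It never ranks a non-responder above a responder and ties them only at exactly 50%.

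**The case against.** **The gain depends on the model.** This stands. The table shows a loss to Yates of about 1-4 points in the switch case for correlations up to 0.8. In an extreme case, where treatment only lifts subjects from just below the cut to exactly 4 weeks, the rank test has about 20-24% power. This argues against replacing the primary test. It does not argue against a supportive analysis, since a divergence between the two would itself be informative.

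**A supportive analysis does not raise primary power.** This also stands. A reader might infer that each cohort gives up 9-12 points of power, or that the trial is underpowered. The documents support neither reading. The primary test keeps 82.5%, the 9-12 points describe a replacement test under one effect model, and about 3 of them are Yates conservatism.

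**The SAP does test weekly data.** Correct. A reader might take "A summary for the subtypes combined will be included. No CIs or inferences will be given" as a bar on all weekly inference. It covers only the by-week responder table.

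**Redaction.** The exploratory analyses cannot be seen, so the gap can be asserted only for the visible text.

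**Another p-value invites rescue of a failed primary.** This is a fair risk, because neither document adjusts for multiplicity (Protocol 10.8, SAP 10.7). It is met by labelling the analysis supportive and saying so in advance.

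**Conclusion.** The point holds as a modest, low-cost improvement. In the visible text, no inferential analysis uses the number of improved weeks or weekly joint-responder status. No planned analysis is invalid, and the primary endpoint, test and alpha should not change.

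Under a common shift with within-subject correlation 0.2-0.8, a rank test would have about 91-95% power against 82.5%. About 6-9 points of the gain come from avoiding the cut and about 3 from dropping Yates. Under a pure switch it would have about 79-82%. Which form is nearer the truth cannot be settled from the documents. The figures also assume 8 evaluable weeks and do not model the 60% rule.

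**What to change.** In SAP 11.2, replace the sentence that rules out CIs and inference on the weekly responder data with one pre-specified supportive analysis in the FAS:

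- **Test.** Within each subtype, compare improved weeks between arms with a Mann-Whitney test at one-sided 0.10. For the subtypes combined, use van Elteren stratified by subtype.
- **Estimate.** Report the probability that a Blautix subject has more improved weeks than a placebo subject (ties counted half), with an 80% CI.
- **Score.** Use the proportion of evaluable weeks improved, with subjects who have fewer than 4 evaluable weeks ranked lowest, in line with Protocol 10.7 and SAP 10.4. As a sensitivity version, use the 0-8 count with non-evaluable weeks as not improved.
- **Status.** Label it supportive and state that it cannot rescue a missed primary.

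The score needs one denominator. Protocol 10.7 applies the 60% rule to evaluable weeks, while SAP 10.1.1 words it for the treatment period. Read literally, the latter gives 0.6 × 8 = 4.8 weeks, out of reach with 4 evaluable weeks. The two should be reconciled.

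The cost is SAP wording and one table from data already derived. Protocol 10.5.2 already allows "the Mann Whitney test or other standard statistical tests as appropriate" for secondary endpoints, so the method is familiar to the plan. The downsides are one more unadjusted p-value and an effect measure less familiar than a difference in responder rates. The change must be in the SAP before database lock and unblinding.
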